5.3 Sample size calculation: The primary outcome for this study is a linear mixed model of GRA variation over time. Weekly GRA and O'Leary-Sant values will be obtained on all participants. We will then further characterize patients as either treatment responder or non-responders, with treatment response defined as "moderate (+2)" or "marked (+3)" improvement on the GRA. We used previously reported outcomes from an RCT regarding impact of medication on ICBPS symptoms.

Given that we will be performing a linear mixed model, we powered our study to detect a 30% change in treatment response between groups on the GRA, with baseline response rate of 26%. We require 41 participants/group (total N=82) to obtain 80% power ($\alpha=0.05$), assuming an effect size of 0.85. Allowing for a dropout rate of 15%, we aim to randomize 94 women (47/group). We will be able to recruit the required number of participants. We see 12-15 new patients with ICBPS per month and should

be able to adequately recruit 6-7 patients/month, allowing us to meet the necessary sample of patients within 14 months of study initiation. Despite COVID-19, we still continue to care for this number of patients. The study has maximized digital & phone contact and minimized in-person contact. We foresee that we should meet our recruitment aims despite the pandemic's restrictions.

6. Study Timelines

6.1 Based on current clinic volume in the UNM division of the Urogynecology, from which we are recruiting, we estimate that recruitment of 60-120 patients will be feasible over approximately 2-3 years. Per chart review, the urogynecology division sees patients who meet criteria for this study at the rate of 10-20 per month. Assuming that approximately 25% of patients will agree to study participation (due to issues of time commitment and eligibility criteria), we believe that we will be able to recruit an appropriate number of patients in approximately 2-3 years. We believe that an additional 3 months will be needed for follow up data. We anticipate that data analysis and manuscript writing will take an additional 6-9 months.

7. Study Endpoints

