Data Analysis: Between and within group differences will be evaluated using chi-square analysis as deemed appropriate by the statistician involved in study analysis (e.g. Fisher's Exact test for non-normal distributions of categorical variables and T-test for continuous variables). Differences between groups will be evaluated using Chi-square analyses for categorical variables as deemed appropriate by the statistician involved in study analysis (e.g. Fisher's Exact test for non-normal distributions). T-tests will be utilized for continuous variables, with comparison by Mann Whitney U for non-normal distributions. Within-group differences over time will be analyzed using the McNemar's test. If any baseline differences exist between the groups, a regression or multivariable analysis will determine the contribution of these differences to observed differences between groups. As the GRA and O'Leary-Sant will be collected more frequently, we plan to analyze these results with linear mixed models analysis.

Power Analysis: Power analysis was performed based on previously reported means and standard deviation from treatment effect based on GRA. We assumed that 41 patients in each arm (total 82) would be required to find a difference of 30% between group's pain scores (the primary outcome) with 80% power and alpha of 0.05. In order to achieve power we will need a total of 82 patients. Assuming an approximate 20-25% dropout or loss to follow-up rate, we will plan to randomize approximately 60-120 patients.

13. Provisions to Monitor the Data to Ensure the Safety of Subjects

A DSMB will not be monitoring safety of these procedures as the study risks are low. The intervention arm includes mindfulness and yoga, both of which have been shown to be low-risk interventions with minimal adverse events^{xix}. The control group will undergo standard of care treatments. Theoretically, there could be increased muscle soreness noted in patients in yoga treatment arm. There are no documented adverse events with mindfulness practice.

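### Section 5.3 quotes an effect size of 0.85 with no scale or SD; read as standardised it contradicts 41 per group, and 94 randomised does not leave the 82 women required

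*Combined protocol and SAP*

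**What the plan says.** Section 5.3 (Sample size calculation) gives the target in terms of responders: "we powered our study to detect a 30% change in treatment response between groups on the GRA, with baseline response rate of 26" per cent. It continues "We require 41 participants/group (total N=82") for 80% power at alpha 0.05, and then adds the effect size and the randomisation target: "assuming an effect size of 0.85. Allowing for a dropout rate of 15%, we aim to randomize 94 women (47/group"). It does not say what scale the 0.85 is on and gives no SD.

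The Power Analysis paragraph, under Data Analysis at the end of section 12, repeats 41 per arm, 82 in total and a 30% difference, "with 80% power and alpha of 0.05". It describes the basis differently: "Power analysis was performed based on previously reported means and standard deviation from treatment effect based on GRA". No mean or SD follows. It assumes 20-25% dropout, against 15% in section 5.3, and gives the number to be randomised as a range of about 60-120.

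**The concern.** An unlabelled effect size in a power statement is normally read as a standardised difference, and this one sits beside a linear mixed model of GRA over time. On that reading it does not agree with the sample size in the same sentence. The two sections also disagree on whether a proportion or a mean was powered, so the calculation as described cannot be reproduced from one set of inputs. The power statement is what a reader will use to interpret a null or a positive result.

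The dropout allowance raises a second question: whether 94 randomised women deliver the evaluable number that the plan says it needs. That depends on which of the two dropout rates applies.

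**Working it through.** **Inputs.** From section 5.3: control response 26%; change of 30%; effect size 0.85; 41 per group, 82 in total; power 80%; alpha 0.05; dropout 15%; 94 randomised. From section 12: 1:1 allocation; dropout 20-25%. Two assumptions: a two-sided test (sidedness is not stated) and an absolute change of 30 points, so 26% versus 56%. Both are supported by the result, because a relative 30% change (26% versus 33.8%) would need 540 per group and a one-sided test 33.

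**Step 1: reproduce 41 per group from the response rates.** Pooled two-proportion formula, mean rate 0.41:

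n = [1.960 × √(2 × 0.41 × 0.59) + 0.842 × √(0.26 × 0.74 + 0.56 × 0.44)]² / 0.30² = (1.363 + 0.558)² / 0.09 = 40.99, so **41 per group**. Power at 41 is 80.0%.

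Arcsine version: h = 2·asin(√0.56) − 2·asin(√0.26) = 1.691 − 1.070 = **0.621**; n = 2 × (1.960 + 0.842)² / 0.621² = 40.7, again 41.

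**Step 2: try 0.85 as a standardised effect.**
- Two-sample t-test with d = 0.85: 22.7, so 23 per group (normal approximation 22).
- Power at 41 per group with d = 0.85: 96.7%.
- Standardised difference detectable with 80% power at 41 per group: 0.626.
- If 0.85 were Cohen's h starting from 26%, the other arm would be at 67.1%, a difference of 41 points rather than 30.

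Other scalings of 26% versus 56% miss 0.85 too: risk difference over SD 0.61-0.64, logit-based d 0.71, log relative risk 0.77, probit difference 0.79, log odds ratio 1.29.

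**Step 3: try 0.85 as a raw difference in GRA points.** For 41 per group the SD would have to be 0.85 / 0.626 = 1.36 (1.37 by the normal approximation). Neither section gives an SD, so this reading is possible but cannot be checked.

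**Step 4: dropout.** 82 × 1.15 = 94.3 matches the stated 94. To retain 82 after 15% loss the divisor is 0.85: 82 / 0.85 = 96.5, so 97, or 98 with equal arms (41 / 0.85 = 48.2, so 49 per group). The target of 94 retains 82 only if loss is at most 1 − 82/94 = 12.8%.

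What 94 delivers, with power for 26% versus 56% by the pooled formula:

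| Loss | Evaluable | Per group | Power | Total needed for 82 |
|---|---|---|---|---|
| 15% | 94 × 0.85 = 79.9, about 80 | 40 | 79.0% | 97 (98 with equal arms) |
| 20% | 94 × 0.80 = 75.2, about 75 | 37.5 | 76% | 82 / 0.80 = 102.5, so 103 |
| 25% | 94 × 0.75 = 70.5, about 70 | 35 | 73% | 82 / 0.75 = 109.3, so 110 |

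At 40 per group the arcsine method gives 79.3% and the exact Pearson calculation 80.0%, so the shortfall at 15% loss is about 2 women and at most about 1 point of power.

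**The case against.** The sample size is not wrong. The response rates, power and alpha in section 5.3 return 41 per group, and neither 41 nor 82 depends on the 0.85. The 30-point difference is stated correctly in the same passage, so a reader who sees both is more likely to be confused than misled. This stands.

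The 0.85 may be a raw GRA difference. Section 5.3 refers to a mixed model of the GRA and an earlier randomised trial, and section 12 refers to means and an SD. An SD near 1.36 would make it agree with 41 per group. This also stands, and it rules out a tempting stronger reading. A reader might infer that the plan overstates its detectable effect by about 36% (0.85 / 0.626 = 1.36). That holds only if 0.85 is standardised, which the documents never say.

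The 15% shortfall is two women and about one point of power, which on its own is a minor note. That is fair. It gains weight only because section 12 assumes higher loss, under which the same 94 falls clearly short.

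What does not fall away: the 0.85 is undefined, its usual reading contradicts the sentence it sits in, the two sections give different bases, and 94 does not yield 82 at any dropout rate the plan states.

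**Conclusion.** Wrong as written, and a reporting correction rather than a flaw in the design. The 41 per group is sound for 26% versus 56% responders (h = 0.62). The 0.85 either contradicts it (standardised: 23 per group needed, about 97% power at 41, detectable effect about 0.63) or depends on an SD of about 1.36 that is not given. The documents do not show which, so it should not be concluded that the sample size is wrong or that the detectable effect is misreported by a known amount.

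The 94 randomised leave about 80 evaluable and about 79% power at 15% loss, or about 70-75 evaluable and 73-76% power at 20-25% loss, against the 82 and 80% stated. These powers assume a two-sided 5% test of 26% versus 56%.

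**What to change.** 1. Ask the sponsor which calculation was done, and keep that one. Either state 26% versus 56% responders (30 points absolute, h = 0.62) and remove the 0.85, or state that 0.85 is a raw GRA difference and give its SD and source. The reference to means and an SD in section 12 should not be deleted before this is answered, since it may be the true basis.
2. Make section 5.3 and the Power Analysis paragraph in section 12 agree on that basis and on one dropout rate.
3. Restate what 94 randomised women deliver at that rate: about 80 evaluable and 79% power at 15%, or about 70-75 and 73-76% at 20-25%. If the basis is the raw difference, recalculate the power from its SD.

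For reference, keeping 82 evaluable would take 49 per group (98 in total, 4 more than planned) at 15% loss, or about 103-110 in total at 20-25%. All of these lie within the stated 60-120 range.

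Steps 1 to 3 change wording only. The cost is that the stated evaluable number and power become slightly less favourable. Raising the target instead would mean recruiting the additional women.

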43. Other Waiver Types (Checklist)	29
44. Vulnerable Populations (Checklist)	29

PROTOCOL TITLE: MYPAICE: Mindfulness and Yoga for Pain with Interstitial
Cystitis Evaluation

45.	Medical Devices (Checklist).....	35
46.	Export Control (Checklist)	36
47.	Data Transfer/Sharing (Checklist).....	36
48.	Specimen Transfer/Sharing (Checklist).....	37

1. Objectives

1.1 The objective of this research is to perform a non-masked, randomized clinical trial to assess pain levels and function and level of care required by patients with interstitial cystitis/painful bladder syndrome (IC/BPS) randomized to treatment with mindfulness and yoga + standard of care compared to standard care alone. Standard of care for IC/BPS is defined as treatments recommended in the American Association of Urology (AUA) guidelines (see Table 1). The target population is patients who have IC/BPS and are willing to be randomized to mindfulness/yoga therapy or standard of care therapies

Table 1: AUA Treatment Guidelines for IC/PBS

First Line	General relaxation/ Stress management, pain management, patient education, self-care, behavioral modification
Second Line	Appropriate manual physical therapy techniques, oral agents including: amitriptyline, cimetidine, hydroxyzine, PPS, intravesical instillation of DMSO, heparin, lidocaine.
Third Line	Cystoscopy under anesthesia with hydrodistension, treatment of Hunner's lesions if found.
Fourth Line	Intradetrusor Botulinum Toxin A, Neuromodulation.
Fifth Line	Cyclosporine A
Sixth Line	Diversion with or without cystectomy, substitution cystoplasty

1.2 Our central hypothesis is that IC/BPS participants treated with yoga and mindfulness will have greater improvement in their symptoms than those treated with standard of care alone. Specifically:

1.3 Outcomes & Hypotheses:

- i) IC/BPS participants treated with mindfulness and yoga will assess their response to treatment based on the Graded Response Assessment (GRA) scale (described below) at 3 months compared to standard care participants.
Hypothesis: IC/BPS participants treated with mindfulness & yoga + Standard of care will have superior scores on the GRA scale compared to those treated with Standard of Care alone.

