- ii) Participants will start with 1st and 2nd Line therapy as recommended by the AUA guidelines (AUA guidelines categorize treatments as 1st through 6th Lines of care) and we will record the numbers of participants that accelerate to higher lines of therapy. *Hypothesis: IC/BPS participants treated with mindfulness & yoga + Standard of care will have fewer participants who accelerate to higher Lines of care compared to those treated with Standard of care alone.*
- iii) Participants will record pain, function and other IC/BPS symptoms using validated questionnaires at baseline and at follow-up (approximately at 6 and 12 weeks of treatment). *Hypothesis: IC/BPS participants treated with mindfulness & yoga + Standard of care will have greater improvement in pain, function and other IC/BPS symptoms compared to participants treated with Standard of care alone, based on validated questionnaires.*
- iv) Cost-analysis will be performed comparing treatment groups. *Hypothesis: Cost analysis will find that those treated with mindfulness & yoga + Standard of care will incur less cost than Standard of care alone.*
- v) Qualitative outcomes will be obtained with an optional response during the weekly interviews to see how participant's feel their treatment is going. At a later time we may go back and enter quotes into qualitative software for analysis of themes. *Hypothesis: Patients in the mindfulness & yoga + Standard of care may feel more empowered about their health.*

2. Background

IC/PBS is a chronic urologic pain disorder associated with significant morbidity. It is defined by the American Urogynecological Association (AUA) as “a complex sensation (pain, pressure, or discomfort) perceived to be related to the urinary bladder, associated with lower urinary tract symptoms of more than 6 weeks duration, in the absence of infection or any other identifiable causeⁱ.” A 2015 survey of 1,982 patients with IC/BPS noted that, of the 180 treatment modalities, none were truly effective. In the survey, patients were surveyed about their usage of complementary and alternative medicine (CAM). Of those who responded, 84.2% had tried CAM and 55% had been recommended CAM by their physiciansⁱⁱ. There are many reasons as to why patients turn to CAM, including side effects experienced from traditional therapies, lack of efficacy and frustration with providersⁱⁱⁱ.

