We will perform an unmasked, randomized controlled trial comparing yoga and mindfulness impact on 1) treatment response 2) level of treatment required 3) pain, activity and quality of life for patients with IC/BPS compared to standard care alone as recommended by the AUA (Table 1). The target population will be those patients with IC/BPS who are cared for by the urogynecology, gynecology and urology specialties. After obtaining informed consent, women will be randomized to either yoga & meditation + Standard of care compared to Standard of care alone. Masking is not possible with this study design, as participants randomized to the yoga/mindfulness versus standard of care will clearly know their treatment arm.

4. Inclusion and Exclusion Criteria

4.1 We will recruit patients who present with IC/BPS per the AUA definition. To confirm the diagnosis of IC/PBS, We will also administer the O'Leary-Sant Interstitial cystitis Symptom Index and Problem Index to determine if patients are candidates for the study. We will also require that they have a physical exam performed in the past 2 years. As documented by others, a domain score of >6 will indicate applicability for enrollment in either symptom or problem domain^{xi}. Additional inclusion criterion include: evidence of an absent UTI (e.g. negative urine

PROTOCOL TITLE: MYPAICE: Mindfulness and Yoga for Pain with Interstitial Cystitis Evaluation

dipstick, a negative urinalysis or urine culture) within 2 months of enrollment as well as ability to speak and understand English or Spanish. We will recruit only patients who will be undergoing first-line and second-line treatment, as defined by AUA and who have not made treatment changes to their regimen in the past 4 weeks.

Patients will be excluded if they have:

- unevaluated hematuria,
- a history of recurrent urinary tract infection (UTI), as defined by AUA criteria as >2 culture-proven UTIs in 6 months or 3 UTIs in one year within the last 5 years,
- urinary retention, defined as a post-void residual (PVR) of >150 mL confirmed by bladder scan or catheterization,
- a history of augmentation cystoplasty or urinary diversion,
- a history of cyclosporine A use
- a history of pelvic radiation or chemotherapy in the past 2 years
- history of radiation induced cystitis
- if patients are currently pregnant or lactating or planning on becoming pregnant in the next 3-4 months

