7.1 The **primary endpoint** of our study is to determine the 3 month Global Response Assessment (GRA) in patients who perform yoga & mindfulness + Standard of care compared to patients who undergo Standard of Care alone, as well as a linear mixed model analysis of the GRA over time. Our **secondary endpoints** include: (i) proportion of patients in each group using accelerated lines of treatment (2-6) based on the AUA guidelines (i) the following validated questionnaires:), O'Leary-Sant Symptom and Problem Index (OSPI/OSCI), patient self-efficacy questionnaire (PSEQ-2), the PROMIS- Pain Interference Short Form 6b (PROMIS-PI and a visual analog scale, and the hospital anxiety and depression scale (HADS-A/D) (iii) Cost analysis potentially using, for example, the QALY scale if funds are found to support this.

7.2 We will not have any primary or secondary safety endpoints for which the study will be powered, as the interventions are extremely low risk (mindfulness and yoga).

7.3 Our **exploratory endpoints** are to investigate compliance to mindfulness and yoga treatment. Due to the extremely low-risk nature of therapeutic interventions, we do not have any safety endpoints.

8. Research Setting

8.1 The study will be performed at the University of New Mexico (UNM) Eubank Women's Primary Care Clinic and Sandoval Regional Medical Center (SRMC) Urogynecology clinics. These Urogynecology clinics are dedicated to care of women with pelvic floor disorders such as interstitial cystitis/bladder pain syndrome (IC/BPS), the target population for this study.

PROTOCOL TITLE: MYPAICE: Mindfulness and Yoga for Pain with Interstitial Cystitis Evaluation

8.2 Potential subjects will be recruited in the UNM Eubank and SRMC clinics when they present for care for IC/BPS, either in person or virtually via telephone or Zoom care visits. All patients will have a history and physical taken to determine their study eligibility, as well as a baseline BPIC-SS. Recruitment will take place either in private exam rooms at these clinics or over HIPAA-compliant telephone or Zoom conversation, and informed consent conversations regarding these clinics will take place via the same means.

8.3 There are no other laboratory tests in this trial other than would be routinely collected in the work up of IC/BPS.

8.4 There will not be involvement of any community advisory board.

8.5 There will not be any research conducted outside of the UNM HSC and its affiliates.

9. Resources Available

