Our primary aim is to determine whether the participants assess themselves as improving following the interventions based on the GRA at 3 months. The target population will be patients with IC/BPS who are seeking care. The current recommendation is to advise patients to undergo conservative management with self-care, behavioral modification techniques. If a patient is interested in this and fulfills study inclusion criteria then we will offer her the choice of volunteering for the study. All women will give consent prior to their enrollment, after they have had time to carefully consider whether they want to participate in the study. Research staff and clinicians will obtain consent either in clinic or via zoom. After enrollment, participants will fill out baseline surveys including:)the O'Leary-Sant Symptom and Problem Index (OSPI/OSCI)Patient Self Efficacy Questionnaire-2 (PSEQ-2), Hospital Anxiety and Depression Scale (HADS-A/D), PROMIS- Pain Interference Short Form 6B (PROMIS-PI), and a visual analog scale

In addition to the above outcomes, we will collect patient demographics, medical/surgical history and information regarding their IC/BPS (e.g. time since IC/BPS diagnosis, previous treatments for IC/BPS tried) and patient contact information. Once this information is collected, patients will also fill out an attestation of use, which they will sign/e-sign in REDCap, an affidavit that if they are randomized to mind/body they will use these daily to the best of their ability.

Randomization: Randomization assignment will be generated by computer generated randomization scheme used by appropriate personnel such as a statistician. Participants will be randomized in a 1:1 ratio by a computer generated sequence at enrollment. Randomization assignments will be completed via REDCAP. Randomization will only occur after consent has been obtained and all baseline data has been obtained.

Interventions:

Yoga & mindfulness meditation + Standard of care: Women will be asked to perform mindfulness meditation via a commercially available smartphone app and yoga through an online video tutorial (designed by a Physical Therapist expert in IC/BPS care and designed specifically for IC/BPS patients). Our online tutorial is currently in the process of being formatted however see supplemental materials for yoga flow. Patients will be instructed to perform

PROTOCOL TITLE: MYPAICE: Mindfulness and Yoga for Pain with Interstitial Cystitis Evaluation

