approximately 10 minutes of meditation daily via a commercially available app (either Calm App or Headspace App, both of which are commercially readily available) and approximately 15 minutes of yoga via the online tutorial. Yoga & use of the meditation app is estimated to take approximately 30 minutes per day. Patients may engage in any other of the 1st Line AUA therapies as well taking over the counter medications (Table 1). Patients will be called weekly to ascertain treatment compliance and monitor their progress. If symptoms are not improving there will be the option to discuss other treatment options (e.g. accelerate to higher lines of therapy based on AUA guidelines) at 6 weeks.

Women assigned to the Standard of Care alone group will receive any 1st Line and 2nd Line treatments (excluding use of the online yoga and meditation app). Patients will also be called weekly to monitor progress and to ensure no treatment effect secondary to phone calls. If symptoms are not improving there will be the option to discuss other treatment options (e.g. accelerate to higher lines of therapy based on AUA guidelines) at 6 weeks. At the termination of the study women in the standard of care group will receive 3 months of Calm App.

At the 6 week follow-up phone call patients will be given the option for escalation of therapy. Patients will be given the opportunity to escalate their treatment for IC/PBS to higher lines of treatments: use of intravesical Botox or use of sacral neuromodulation. We will record any accelerated therapy used by the patient that may be added during study participation.

For participants who have completed the study but treatment escalation data was not properly captured in RedCap surveys, These participants will be notified via email through RedCap to complete this additional survey.

Outcome measures:

GRA: The Global Response Assessment is a validated tool to assess response to treatment. It is comprised of a single question and has been utilized widely in IC/BPS^{xiii}. This will be collected weekly. However, the primary outcome is the 12 week (3 month) result.

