THERAPY ESCALATION: We will record when and what women use that is greater than 1st line and 2nd line therapies during their participation in the study. They will discuss escalation of therapy with their provider and study personnel will record the additional therapy as an outcome measure. This will be utilized to perform cost utility analysis to determine if the intervention is cost-effective.

PSEQ-2: The Patient Self-Efficacy Questionnaire Short Form is a 2 question questionnaire that has been used in multiple chronic pain conditions to

PROTOCOL TITLE: MYPAICE: Mindfulness and Yoga for Pain with Interstitial Cystitis Evaluation

document feelings of self-efficacy. The Short form is validated in chronic pelvic pain^{xiv}. This will be collected at baseline and at 12 weeks.

PROMIS-PI: The PROMIS-Pain interference short form 6B is an NIH PROMIS measure that measures the extent that pain interferes with daily activities. It is comprised of 6 questions^{xv}. This measure will be collected weekly.

HADS: This is formally called Hospital Anxiety/Depression Scale. This is a 7 item inventory that assesses generalized anxiety including: tension, worry, fear, difficulty relaxing and restlessness^{xvi}. This measure will be collected at baseline and at 12 weeks.

Euroqol-5d. (EQ-5d) This is a validated measure utilized to measure health states^{xvii}.

O'Leary-Sant Interstitial Cystitis Symptom and Problem Index:

This validated survey assesses severity of symptoms and bother in IC/BPS and is commonly used for IC/BPS trials. Symptom index, which has been explicitly analyzed in a prospective trial to detect change, and problem index are to be separately analyzed^{xviii}

Data Analysis

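### Secondary endpoint (i) in section 7.1 counts AUA lines 2-6 as escalation, whereas hypothesis ii and the therapy-escalation outcome in section 12 set the threshold above the second line

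*Combined protocol and SAP*

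**What the plan says.** Section 7.1 gives the first secondary endpoint as the "proportion of patients in each group using accelerated lines of treatment (2-6) based on the AUA guidelines". Other places in the same document put the threshold elsewhere or describe second-line therapy as background:

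- Section 1.3 (ii): "Participants will start with 1st and 2nd Line therapy as recommended by the AUA guidelines", and "we will record the numbers of participants that accelerate to higher lines of therapy". Hypothesis ii is stated on that basis.
- Section 4.1: "We will recruit only patients who will be undergoing first-line and second-line treatment, as defined by AUA".
- Section 12, Interventions, control arm: "Women assigned to the Standard of Care alone group will receive any 1st Line and 2nd Line treatments". The escalation offered at the 6-week call is described as a move to higher lines, and the examples named are Botox and sacral neuromodulation. Table 1 lists botulinum toxin and neuromodulation as fourth line.
- Section 12, the therapy-escalation paragraph under Outcome measures: "We will record when and what women use that is greater than 1st line and 2nd line therapies during their participation in the study".

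Table 1 shows what the second line contains: "Appropriate manual physical therapy techniques, oral agents including: amitriptyline, cimetidine, hydroxyzine, PPS", and intravesical instillations.

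Two places point to a lower background. The yoga-arm text in section 12 mentions other first-line therapies and over-the-counter medication without naming the second line. Section 18 describes enrolled patients as opting for first-line treatment. Yet that arm's own heading is "Yoga & mindfulness meditation + Standard of care".

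**The concern.** An endpoint definition has to say which events count and from when. Here the endpoint section and the hypothesis it is meant to test disagree on the threshold by one line of therapy. The line in dispute covers common, easily started treatments, so it could supply a material share of the events. Section 7.1 also gives no start-date rule that separates therapy begun during the study from therapy already in use.

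Two analysts working from this protocol could report different escalation results. The trial is unmasked, so a threshold chosen after the data are seen would be open to challenge. Level of care required is part of the stated objective in section 1.1 and the second of the three comparisons listed in section 3. The therapy-escalation paragraph of section 12 also feeds these data into the cost-utility analysis, which is affected only if that analysis adopts the 7.1 definition.

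**Working it through.** **Step 1: the texts side by side.** The documents state no expected rate, power or sample size for this endpoint, so there is no figure to reproduce. The check is which events each text counts.

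| Event during the study | Section 7.1 (lines 2-6) | Section 1.3 (ii) (above the starting lines) | Section 12, therapy escalation (above second line) |
|---|---|---|---|
| Starts a third- to sixth-line therapy | counts | counts | recorded |
| Newly starts a second-line therapy | counts | does not count | not among what it says will be recorded |
| Continues second-line therapy in use at randomisation | no rule given; the word accelerated suggests not | does not count | not among what it says will be recorded |

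The second row is the contradiction. It remains even on the reading most favourable to 7.1, in which accelerated means newly added.

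**Step 2: is the background agreed?** Sections 1.3 (ii) and 4.1 and the control-arm text include the second line. The yoga-arm text and section 18 name only the first. If the background were first line only, 2-6 would be a coherent threshold. If it is first and second line, it is not. The documents do not settle this.

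**Step 3: illustration of size.** Every rate below is assumed.

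- n = 41 per arm, from section 5.3, where it was derived for the GRA and not for this endpoint.
- e = probability of therapy above the second line. For the illustration this is taken as true escalation.
- q = probability of newly starting second-line therapy, equal in both arms and independent of e.
- Rate counted under 2-6 = q + (1 - q) × e.
- Test: uncorrected two-sided Pearson chi-square at 5% (critical value 3.84), the test family named under Data Analysis. Power is the exact sum over all pairs of binomial outcomes. Fisher's exact test is the check.

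With e = 35% (control) vs 10% (yoga), a pair chosen because it gives about 80% power:

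| q | Control rate counted | Yoga rate counted | Difference | Chi-square power | Fisher power |
|---|---|---|---|---|---|
| 0 | 35.0% | 10.0% | 25.0 points | 81% | 73% |
| 5% | 0.05 + 0.95 × 0.35 = 38.25% | 0.05 + 0.95 × 0.10 = 14.5% | 23.75 points | 70% | 62% |
| 10% | 0.10 + 0.90 × 0.35 = 41.5% | 0.10 + 0.90 × 0.10 = 19.0% | 22.5 points | 61% | 52% |

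Other assumed pairs, chi-square power at q = 0, 5% and 10%:

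- 30% vs 10%: 65%, 53%, 45%.
- 40% vs 15%: 74%, 65%, 58%.

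**The case against.** The best defence is that the intent can be read from the rest of the document. Section 1.3 (ii) and the therapy-escalation paragraph both put the threshold above the second line, and the 6-week text names fourth-line options. On that view 2-6 is a slip in one parenthesis of an unpowered secondary endpoint. This may be so, but the first-line wording in section 18 and in the yoga-arm text would make 2-6 deliberate, and a reader cannot tell which was meant.

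The illustration can also be attacked, fairly. It treats escalation above the second line as the truth, which is the question left open. If new second-line starts reflect real treatment need, counting them could add signal. The lead rates were selected, and no planned power is lost because none was planned.

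Three stronger readings might be inferred, and the documents do not support them:

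- *The 2-6 count cannot be produced.* The therapy-escalation paragraph does not limit recording to what it lists. The Interventions text also says that any accelerated therapy added during participation will be recorded, and previous treatments are collected at baseline. The survey forms are not in the documents. New second-line starts may go uncaptured; more than that cannot be said.
- *Second-line therapy is assigned to controls alone, so the endpoint is biased towards yoga.* Section 1.1 defines standard of care once, through Table 1; both arms receive it; and section 1.3 (ii) starts all participants on first and second line. Section 9.2 says the research protocol requires no ordering of therapeutics. The arm-specific wording is an ambiguity and does not establish a difference in use.
- *Stable baseline second-line therapy is counted as escalation.* Much larger distortions follow only on this reading, which goes against the natural sense of accelerated and against the section 12 reference to therapy added during the study.

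**Conclusion.** The contradiction stands and rests on the text alone. As written, 7.1 counts newly started second-line therapy as escalation; section 1.3 (ii) and the therapy-escalation paragraph of section 12 do not. The background lines are themselves described inconsistently, so correcting one number in 7.1 without settling them would leave the ambiguity in place.

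The size is unknown. The fall from 81% to 70% or 61% holds only for the assumed rates, with equal and independent second-line starts in each arm and true escalation taken as above the second line. It shows that a few such starts could matter, and it is not an estimate for this trial. The primary GRA endpoint and its sample size are untouched. The point should be fixed because a secondary hypothesis depends on it and rewording is cheap.

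**What to change.** The sponsor should first reconcile what sections 1.3 (ii), 4.1, 7.1, 12 (both arms and the therapy-escalation paragraph) and 18 say about background therapy. This review does not say which lines are right.

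Then use one definition in 7.1, hypothesis ii and section 12, identical in both arms: the proportion of participants who, after randomisation and by week 12, start a therapy above the reconciled background lines, with therapy already in use at randomisation not counted.

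- If sections 1.3 (ii) and 12 (therapy escalation) stand, the 2-6 in 7.1 must change.
- If newly started second-line therapy is meant to count, those two sections must change, and such starts must be recorded with dates.

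The cost is a rewording and, if second-line starts are to be recorded, one dated item in the existing weekly calls. For women who have already completed, the catch-up survey described in section 12 could carry the item, with some recall error. If the threshold settles above the second line, fewer events may count than under 2-6. No extra participants or visits are needed.
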